#### Summary Statistics for Demographic and Clinical Data

Demographic characteristics and medical history will be summarized, e.g., proportion, mean, median, standard deviation, and minimum and maximum values. Means and standard deviations will be reported for all continuous variables; percent will be reported for categorical variables.

# Sample Size Justification

Given the high-throughput data generation strategy of next-generation sequencing, the use of different starting materials for sequencing (mRNA, small RNA, DNA), and the use of serial sampling, standard sample-size calculation methods are not appropriate in this case and an adaptive study design is a more realistic approach. Sample size consideration will be based primarily on the power to identify differentially expressed genes. A recent pilot study of glucocorticoid action performed by the NIH Center for Human Immunology (CHI) (32) administered intravenous hydrocortisone at doses of 50 or 250 mg to a group of 20 healthy volunteers, where 10 subjects received each dose. They performed transcriptional analysis by expression microarrays in PBMCs before and at six time points after the infusion. They used the R package limma for analysis, which implements linear models and empirical Bayes methods for assessing differential expression in microarray experiments (33). P-values underwent multipletesting correction using the method of Benjamini and Hochberg to estimate the false-discovery rate (FDR). Using cut-off values of < 5% FDR-adjusted p-value and > 0.5 absolute average log2fold-change, they found evidence of differential expression in over 400 genes at the lower dose and over 600 genes at the higher dose, with a maximum number of differentially expressed genes 4 hours after the infusion for both doses. This was accomplished with only 10 subjects per dose,

despite technical difficulties (notably hemolysis), and the use of hydrocortisone (which is approximately five times less potent than methylprednisolone, the glucocorticoid we plan to use in our study). In addition, the data from the study by Olnes et al. used bulk PBMCs, which are likely to give a more variable expression signal than the purified cell sub-types that we plan to employ in our study. Based on this information, we estimate that an initial recruitment of at least 20 subjects is likely to reveal the changes in gene expression over time that our study aims to define in individual cell sub-types. We propose an adaptive study design, in which we will recruit an initial cohort of 20 subjects. Based on the observed data from 20 subjects, we will then assess the conditional power that can be obtained with up to 30 additional subjects. We will also perform a bootstrap procedure, sampling with replacement up to 50 units from the 20 observed subjects, to evaluate the improvement in gene detection. For example, if the number of genes that can be detected reaches a plateau after 30 subjects, we will stop at that number. However, if the number of detected genes is seen to rise with a sample size of 30, but the pathways and the biological interpretation of the data remain unchanged, additional subjects will be unlikely to change the outcome of the study and no further recruitment will be pursued. Due to the adaptive sample size determination, we will use a nominal significance level  $\alpha < 0.05$ .

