	5 mL: Complete blood count, acute care panel and serum pregnancy test	NA	
		5 mL: Serum	Concentration of methylprednisolone
	infusion whole-	60 mL: Isolation of hematopoietic cell sub-types (e.g. neutrophils, B cells, CD4+ T cells, CD8+ T cells, monocytes, NK cells)	RNA-level, DNA-level, protein-level, and/or functional assays
		10 mL: PBMC isolation	PBMC banking
		8 mL: Plasma purification	Plasma banking
		5 mL: Complete blood count and acute care panel	NA
		5 mL: Serum	Concentration of methylprednisolone

**Table 2.** Processing and use of samples from healthy volunteers

aThe purpose of this initial sample will be to assess the level of variation in the baseline.

Abbreviations: iPS induced pluripotent stem (cells), NA not applicable, NK natural killer, PBMC: Peripheral blood mononuclear cell, TBNK: Flow cytometry panel for T lymphocytes, B lymphocytes, and NK cells

Volunteers will be discharged after collection of the 2-hour or 4-hour blood and biopsy samples (depending on the regimen of blood collection), measurement of vital signs, and documentation of any AEs. Follow-up phone calls 1 day and 5 days after discharge will document any adverse effects related to the drug or skin biopsy. If any AEs that may require treatment are documented on the follow-up phone calls, volunteers will be asked to come to the NIH CC's outpatient clinic for evaluation by the Principal Investigator.

We propose an adaptive study design, in which we will recruit an initial cohort of 20 subjects. After processing the samples from these subjects, we will perform differential expression analysis to determine if recruitment of additional subjects (up to a maximum of 50) would impact the biological interpretation of the data. If additional data would be unlikely to change the study outcome, then no further recruitment will be pursued.

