# **Differential Expression Analysis:**

Differential expression analysis for the RNA-seq data will be performed with the software program Cuffdiff (25). In short, the Cuffdiff algorithm models how variability in the measured fragment counts for a transcript depends on its expression level as well as its splicing structure. The algorithm captures uncertainty in a transcript's fragment count as a beta distribution and the overdispersion in this count (determined by globally fitting the observed variance in fragment counts as a function of the mean across replicates) with a negative binomial distribution. Under the resulting beta negative binomial model of fragment count variability, it estimates count variances for each transcript in each sample. These variance estimates are used for statistical testing to report significantly differentially expressed genes and transcripts. Raw p-values and False Discover Rate (FDR)-based q-values (30) are reported.

Differential expression analysis for the small-RNA-seq data will be performed in R, with the package DESeq (31). In short, the DESeq algorithm models fragment count data with a negative binomial distribution and a shrinkage estimator for the distribution's variance. Our choice of this algorithm for the small-RNA-seq data is based on the fact that most human small RNA molecules are not spliced, and DESeq uses raw fragment counts, without the assumption of spliced transcripts employed by the Cufflinks/Cuffdiff algorithms.

For each cell type, we will assess the level of variation in the baseline measurements by comparing the expression values on the day of the screening visit to the 0-hour (pre-infusion) values on the day of the glucocorticoid infusion. We will then perform differential analysis comparing each of the two post-infusion time points (2 hours and 4 hours), independently, against the baseline. We will employ a cutoff value of < 5% FDR to select the transcripts that will be considered differentially expressed in each cell type at each time point. The resulting gene lists will be contrasted to determine, for example, which genes are uniquely differentially expressed in a specific cell type, or common to a specific hematopoietic lineage (myeloid or

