lymphoid). They will also be used for pathway enrichment analysis, to determine the molecular pathways and biological functions that are most responsive to the glucocorticoid stimulus in each cell type. The genes and pathways that are found to be modified by the glucocorticoid stimulus in immune cells but not in non-immune cells (skin cells from this in vivo study and the primary human cells we have studied in vitro), will be selected as the top candidates for targeted therapeutic intervention, which we expect will form the basis of future studies.

Sequencing library preparation and sequencing batches will be carefully designed such that samples from the same subject and cell type are run in the same batch and samples from different subjects are evenly distributed across batches. This will keep batch effects to a minimum in the identification of differentially expressed genes. For analyses across different subjects, such as comparisons among different cell types, linear regression will be adopted with batch as regression variable to adjust for batch difference. While prior experience suggests that library preparation is the greatest source of batch-to-batch variation in RNA-seq experiments, if the source of batch effects is unclear or cannot be adequately modeled, the R package SVA will be used.

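### The 20-subject bootstrap for setting sample size is not calibrated: its false-positive rate rises with the number drawn, so a gene-count plateau read from it is unreliable, badly so if the test is paired

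*Combined protocol and SAP*

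**What the plan says.** Section 14 (Sample Size Justification) sets the sample size in stages. After the first 20 subjects the team will look at conditional power for as many as 30 more, and will also run a bootstrap, "sampling with replacement up to 50 units from the 20 observed subjects, to evaluate the improvement in gene detection". The stopping example is: "if the number of genes that can be detected reaches a plateau after 30 subjects, we will stop at that number". A further branch ends recruitment even though the count is still rising at 30, provided pathways and interpretation do not change. Section 3 gives the purpose of the look as "to determine if recruitment of additional subjects (up to a maximum of 50) would impact the biological interpretation of the data".

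Detection is defined under Differential Expression Analysis: "We will employ a cutoff value of < 5% FDR to select the transcripts that will be considered differentially expressed in each cell type". The contrast is described as "comparing each of the two post-infusion time points (2 hours and 4 hours), independently, against the baseline". Cuffdiff is named for RNA-seq and DESeq for small RNA, with no subject term described for either. The same section arranges batches so that "samples from the same subject and cell type are run in the same batch".

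The plan does not define a plateau numerically, and it does not say how detections in draws larger than 20 are to be calibrated.

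**The concern.** A with-replacement draw of 50 from 20 people contains on average 20 × (1 − 0.95^50) = 18.5 distinct people, but the test is run as if there were 50. The chance error of the original 20 is carried over whole while the standard error shrinks. Transcripts that look changed by luck in the 20 look more convincingly changed in each larger draw, so the detected count can keep rising after the true count has gone flat.

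The bootstrap feeds the decision whether to infuse, and possibly biopsy, up to 30 further healthy volunteers, for whom Section 8.2 foresees no benefit.

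**Working it through.** There is no stated calculation to reproduce. The maximum is 20 + 30 = 50, without an effect size, SD, power or formula.

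**Inputs.** From Section 14: 20 observed subjects, draws of m up to 50, FDR below 5%, nominal level 0.05 (two-sided assumed). Assumed, because the documents give no value: rho, the correlation between a subject's baseline and post-infusion expression, at 0.5, 0.7 and 0.8.

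**Step 1: null variance.** Take a transcript with no response and per-subject change variance s². The mean change over m draws has variance of about s²/20 (error of the observed 20) + s²/m (resampling). A paired test assumes s²/m, so its statistic has variance of about 1 + m/20. An unpaired test ignores the correlation, which gives (1 − rho)(1 + m/20). With m genuinely new subjects these would be 1 and 1 − rho at every m. From m = 20 to 50 the bootstrap factor goes from 2 to 3.5, and 3.5/2 = 1.75.

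**Step 2: null rejection at nominal 5%**, as 2 × (1 − Φ(1.96/√variance)):

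| Test | m=20 | m=30 | m=40 | m=50 |
|---|---|---|---|---|
| Paired | 16.6% | 21.5% | 25.8% | 29.5% |
| Unpaired, rho 0.5 | 5.0% | 8.0% | 11.0% | 13.8% |
| Unpaired, rho 0.7 | 1.1% | 2.4% | 3.9% | 5.6% |
| Unpaired, rho 0.8 | 0.2% | 0.6% | 1.1% | 1.9% |

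With real subjects the paired rate is 5% at every m. The unpaired rates are 0.56% at rho 0.5, 0.03% at 0.7 and under 0.01% at 0.8. The unpaired bootstrap sits at 5% only where rho = m/(m + 20), that is 0.50, 0.60, 0.67 and 0.71 for the four values of m. No single rho calibrates the whole curve.

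**Step 3: gene counts when the truth is nearly flat.** Simulated negative-binomial counts: 12,000 independent genes, 600 changed two-fold, dispersion 0.05, Benjamini-Hochberg at 5%, 4 data sets × 3 bootstraps. The paired test is a t-test on log ratios and the unpaired test a Wald test; both stand in for Cuffdiff and DESeq.

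| Setting | m=20 | m=30 | m=40 | m=50 | Bootstrap rise, 30 to 50 | Real samples |
|---|---|---|---|---|---|---|
| Paired, rho 0.5 | 1,053 | 1,608 | 2,142 | 2,703 | 68% | 628–636 |
| Unpaired, rho 0.5 | 662 | 771 | 913 | 1,137 | 47% | 600–601 |
| Unpaired, rho 0.7 | 592 | 647 | 663 | 740 | 14% | 588, 600, 600, 600 |
| Unpaired, rho 0.8 | 504 | 588 | 610 | 629 | 7% | 509, 591, 599, 600 |

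Of the 2,703 paired detections at m = 50, 2,103 are false. At rho 0.8 about 1.5% of the 7% rise is real (591 to 600), so the spurious part is about 5%.

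**Step 4: gene counts when the truth is still rising.** A separate simulation used normal log-expression, t-tests, and 10,000 genes with 10% changed.

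- Paired, rho 0.5: real counts are 476, 594, 660, 706; bootstrap counts are 913, 1,510, 2,010, 2,535. The false share is 40–71%, against 4–5% in real samples.
- Unpaired, rho 0.5: from m = 30 to 50 real counts rise from 418 to 544 (30%), bootstrap counts from 588 to 1,016 (73%).
- Unpaired, rho 0.8: real counts rise from 415 to 544 and bootstrap counts from 447 to 588, about 31% each.

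**Step 5: split regimens.** Blood is taken under one of two timing regimens. If only 10 of the 20 supplied a given time point (an assumed split), the paired factor at m = 50 would be 1 + 50/10 = 6, and null rejection about 42%.

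**The case against.** Unpaired is the literal reading, since neither Cuffdiff nor DESeq is described with a subject term and the batching sentence is about batch effects, not pairing. On that reading with rho 0.8, bootstrap counts are never more than 5% from the real ones and null rejection stays under 5%. This stands, so the severe figures are conditional on a paired test. The bias is still material at rho 0.5 and 0.7.

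The plateau is only an example. Conditional power and the unchanged-pathways branch can also stop recruitment, and no excess can pass the stated maximum of 50. That is correct, and the effect on the combined decision was not simulated. But conditional power is named without a hypothesis or effect size. Nor does the plan separate the pathway check from the resampled lists, so false genes may reach it too; that is plausible but was not computed.

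Where the true count is still rising, the bootstrap exaggerates the gain without reversing its direction. This also stands.

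A fold-change floor might seem to cure the problem. The cited hydrocortisone pilot had one: "Using cut-off values of < 5% FDR-adjusted p-value and > 0.5 absolute average log2fold-change". In the paired case at dispersion 0.05 (mean count 200 assumed) the floor does flatten the curve, to 613, 604, 603, 601. At dispersion 0.4 it fails, with counts rising from 810 to 2,185. It cannot be relied on alone.

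**Conclusion.** The concern holds, and the plan should be changed before the 20-subject look. Under either test the bootstrap's null variance grows by 75% from 20 to 50 draws, so its gene-count curve does not show what new subjects would yield. The distortion is severe if the test is paired, substantial if unpaired at rho 0.5, moderate at 0.7 and small at 0.8. The plan leaves that choice open.

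The error in the count leans towards recruiting more than needed; its effect on the full decision is inferred. The final lists come from real subjects and are not affected. The null rates rest on a normal approximation and assumed rho. The counts also assume independent genes and stand-in tests, so exact figures would differ with Cuffdiff and DESeq, but the mechanism would not.

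**What to change.** 1. State whether each time point is tested against baseline within subject.
2. Do not count detections in with-replacement samples larger than 20.
3. Subsample without replacement within the 20 (for example 8, 10, … 18 subjects, keeping each subject's time points together) to see whether the count has already levelled off. In tests with paired t-tests, subsamples of 12, 14, 16 and 18 gave 625, 630, 628, 631 where the truth was flat and 132, 177, 211, 243 where it was rising.
4. Project to 30–50 by simulating new subjects from a model fitted to the 20, with shrunken effects and null genes kept null. Accept the model only if it reproduces the observed count at 20, and report the projection's uncertainty.
5. Run the pathway check on the same calibrated lists.
6. Fix a numerical plateau criterion before the look, no finer than the projection's own error.

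As an optional secondary display, show transcripts that also exceed the pilot's 0.5 log2 fold-change floor.

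The cost is SAP wording and some code, with no extra subjects. The drawback is imprecision. Projections to 50 averaged 644 against a true 629 and 410 against 405, but single runs missed by up to 14%, and correlated genes would widen that. This was tested only with paired t-tests and independent genes. The check at 20 matters: a cruder effect model projected 793 where the truth was 628, but it also gave 507 against 629 at 20 and would have been rejected. The accepted model gave 635 against 632.

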# 14 Statistical Considerations

# **Definition of the Study Endpoints**

- The primary endpoint of this study is a set of lists of human genes and non-coding RNAs (small RNAs and lncRNAs) that are differentially expressed in vivo after a glucocorticoid stimulus in each of six immune cell types (B cells, CD4+ T cells CD8+ T cells, NK cells, neutrophils, and monocytes) and one non-immune tissue (skin).
- The secondary endpoint is a list of the genes and molecular pathways that represent the best candidates for targeted therapeutic alternatives to glucocorticoids.

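### The pathway-stability branch lets recruitment stop while the primary gene lists are still growing, and absence from an incomplete skin list then counts towards calling a gene immune-only

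*Combined protocol and SAP*

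**What the plan says.** **Endpoint.** Section 14, Definition of the Study Endpoints: "The primary endpoint of this study is a set of lists of human genes and non-coding RNAs" that change after the glucocorticoid in six immune cell types "and one non-immune tissue (skin"). Pathways enter one level down: "The secondary endpoint is a list of the genes and molecular pathways" judged the best therapeutic candidates.

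**Stopping rule.** Section 14, Sample Size Justification, rests sample size mainly on power to find differentially expressed genes. After 20 subjects, conditional power and a bootstrap of up to 50 units are examined. Two examples follow. In the first, "if the number of genes that can be detected reaches a plateau after 30 subjects, we will stop at that number". The second applies "if the number of detected genes is seen to rise with a sample size of 30, but the pathways and the biological interpretation" hold steady. The stated consequence is that "additional subjects will be unlikely to change the outcome of the study and no further recruitment will be pursued". Section 3 puts the general test as whether more subjects "would impact the biological interpretation of the data". Neither section defines biological interpretation or sets a threshold for calling it unchanged.

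**Candidate selection.** Section 14, Differential Expression Analysis, cuts each list at 5% FDR by cell type and time point and contrasts the lists. Top candidates are genes and pathways changed in immune cells but not in non-immune cells, the latter being skin from this study and primary human cells already studied in vitro.

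**Skin sampling.** Sections 3, 6.2 and 7 make biopsy optional and take it from some volunteers. No minimum number of skin pairs is stated.

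**The concern.** The second example equates stable pathways with a settled study outcome. On the plan's own definition the outcome is the gene lists, and in that example they are still lengthening. The branch that applies while the primary endpoint is moving is thus decided on a secondary, interpretive quantity.

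The consequence has a direction. Candidates are found by subtracting lists, so a gene that responds in both tissues but has reached significance only in an immune cell type looks immune-specific as far as skin is concerned. Pathways can look stable while the skin list is short, and the rule has no criterion for skin, the list likely to have the fewest pairs. At stake is whether a gene is put forward as a target that spares non-immune tissue when it was merely undetected there.

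**Working it through.** **The plan's figures.** The initial 20 and maximum 50 are linked only by 20 + 30 = 50. They rest on analogy with a hydrocortisone microarray study in bulk PBMCs (10 subjects per dose, over 400 and over 600 genes). No power, SD or effect size is given for this trial, so neither number can be reproduced by formula. What follows is illustration.

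**Assumptions.** A paired t-test stands in for the plan's software; m = 15,000 transcripts; D = 400 or 600 detected at 5% FDR, borrowed from that study and held fixed across n; standardised paired effect d = 0.5, 0.7 or 1.0.

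**Per-transcript cut-off.** Solve a(m − D) / [a(m − D) + D] = 0.05, so a = 0.05D / [0.95(m − D)].
- D = 400: 20 / (0.95 × 14,600) = 0.00144
- D = 600: 30 / (0.95 × 14,400) = 0.00219

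**Share missed in skin.** Power = P(|T| > t critical at two-sided a), with T noncentral t, n − 1 degrees of freedom and noncentrality d√n. Share missed = 1 − power. If detection in the two tissues is independent, this is also the share of shared genes detected in an immune cell type that pass the skin part of the filter.

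| Skin pairs | d = 0.5 | d = 0.7 | d = 1.0 |
|---|---|---|---|
| 15 | 92–94% | 78–83% | 43–50% |
| 20 | 86–89% | 62–68% | 20–25% |
| 30 | 71–75% | 32–38% | 2–4% |
| 50 | 38–43% | 5–7% | about 0% |

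The row for 15 is what a stop at 30 gives if half the volunteers have skin taken.

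**Cross-check with other assumptions.** Take 20,000 transcripts, 600 truly responsive, 80% power: a = 0.05 × 600 × 0.8 / (0.95 × 19,400) = 0.0013. With a true log2 fold-change of 0.5 and paired SD of 0.5, 0.75 or 1.0, the share missed at 30 pairs is 4%, 45% or 76%; at 15 pairs it is 52%, 86% or 95%.

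**Share versus number.** With one immune cell type and equal d and n in both tissues, the chance that a shared gene is found in immune cells and missed in skin is power × (1 − power), using the first set of cut-offs:
- d = 0.7: 0.22–0.24 at n = 20, 0.22–0.24 at n = 30, 0.05–0.06 at n = 50
- d = 0.5: 0.19–0.21 at n = 30, 0.24–0.25 at n = 50

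So the share of detected shared genes that look immune-only always falls as n grows, but their number need not, because the immune lists lengthen too.

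**The case against.** Several points on the other side are sound.

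- **The rule is conditional and illustrative.** It requires unchanged pathways and interpretation, both cases are offered as examples, and the plateau example takes the trial beyond 20 subjects. The primary objective is the immune versus non-immune difference, so a material change in that contrast could count as a change of interpretation. This stands as a possible reading, but nothing in the text secures it.
- **A pathway brake is defensible.** Gene counts tend to keep growing with n, and these are healthy volunteers with no prospect of benefit. A reader might infer that the stop must instead be tied to gene-count gain. The documents do not compel that, and it could expose up to 30 more people to the infusion.
- **A gene missed in skin is not automatically a candidate.** The in vitro cells are a second filter, functional validation is a secondary endpoint, and candidates are meant to feed later studies. This lowers the harm without removing it.
- **List subtraction and optional biopsy are the main cause.** Both persist at 50 subjects and after a true plateau. This stands: stopping early aggravates the problem but does not create it.
- **A rise in the bootstrap count is weak evidence.** In a small simulation (8 data sets, 20,000 transcripts, 600 responsive, SD 0.75), 50 real subjects gave about 536 true and 27 false genes, while resampling 50 from 20 gave about 522 true and 3,380 false. A rise may be partly artefact, so the projection needs care.

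**Conclusion.** The mismatch holds on the documents alone: the stopping example treats the outcome as settled while the lists that define the primary endpoint are still growing, and its test, unchanged biological interpretation, is undefined. Because absence from the skin list is part of candidate selection and skin n has no floor, shared genes missed in skin pass that part of the filter.

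The size is not known. At 30 skin pairs the illustration runs from 2–4% to 71–75% of shared genes missed as the assumed effect falls from 1.0 to 0.5; even at 1.0 it is 43–50% if only 15 give skin. The harm is small only with large effects and nearly complete skin sampling, and the plan secures neither.

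Two stronger readings are not supported. A reader might infer that about a third of responsive skin genes would be lost at 30; that holds only for an assumed effect of 0.7. A reader might also infer that early stopping always yields more false immune-only genes; it raises their share among detected shared genes, not always their number.

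**What to change.** 1. In Sample Size Justification, and to match in section 3, state that if recruitment stops under the pathway-stability branch, conclusions are drawn at pathway level and the gene lists are reported as incomplete.
2. In Differential Expression Analysis, do not call a gene immune-only because it is absent from the skin list. Require either a direct immune-versus-skin comparison of the response, or a confidence bound that excludes a relevant response in skin, with relevance defined beforehand.
3. At the 20-subject look, report the projected gain and the number of paired samples for each primary list, skin included, noting that a bootstrap from 20 subjects can inflate gene counts.

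The cost is a narrower gene-level claim under that branch and a little more analysis. The maximum stays at 50 and no additional volunteers are required.
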